1. BACKGROUND AND RATIONALE

Surgery has been associated with short and long-term changes in cognition (postoperative cognitive dysfunction, POCD).^{1,2} The literature shows that most often patients show POCD during the first 1-3 months after surgery, and then recover.³ However, in the recently published NeuroVISION study, up to 30% of 65 years old or older people undergoing different types of noncardiac surgery presented a decline of ≥ 2 points in their Montreal Cognitive Assessment (MoCA) score at 1 year after surgery compared to prior to surgery.⁴ A ≥ 2 points in MoCA score has been shown to correspond to cognitive decline based on formal neuropsychological testing and to be of clinical significance.^{5,6} The risk factors and determinants of POCD are poorly understood.⁷

Chronic pain has been associated with cognitive dysfunction, in particular memory and concentration deficits.⁸ The existing literature on chronic pain in general supports the hypothesis of a bidirectional interaction between pain and cognitive processing.⁸ However, in a longitudinal community-based study, a history of persistent pain (of any origin) at baseline was associated with memory decline, and even dementia, over 10 years of follow-up.⁹ We hypothesize that a similar association might exist between post-surgical pain, and in particular chronic post-surgical pain (CPSP) and POCD (**objective 1**). A surgical population including older ages and with an expected high prevalence of CPSP, like patients undergoing total knee and hip replacement,¹⁰ seems a suitable population to evaluate this association. In this population, up to 23% of hip replacement and 34% of knee replacement surgery patients experience long term pain after surgery.¹¹ The long-term need of analgesic therapy, and in particular, the chronic use of opioids in patients with CPSP, could also play an independent role in mediating the association between CPSP and cognitive changes. Overall, the existing literature on the association between CPSP and POCD, including the role of long-term opioid use, is very scanty and controversial.¹¹⁻¹³

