3.5 Sample size

The ArthroCaP study has been designed as a proof-of-concept study, hypothesis-generating, with exploratory objectives. Based on the original recruitment rate in the main SPOC study, we expected to be able recruit in the sub-study ≥ 150 of the planned 388 SPOC participants. Although exploratory, enrolling ≥ 150 participants would give us a power of $\geq 80\%$ to detect an association between moderate-severe CPSP at 6 months and ≥ 2 point decline in MoCA at 1 year, with an Odds Ratio of 2.5-3.0 when we consider some residual correlation between independent variables (i.e., $R^2 \leq 0.3$ even after removing collinear covariates. This was based on the assumptions that 20% of the study participants will experience ≥ 2 point decline in MoCA at 1 year (considering the possibly younger age and different surgery representation in our study compared to NeuroVISION-1), and that 30% will present moderate-severe CPSP at 6 months (see sample size calculation for the main SPOC study).

Due to the disruptions to recruitment secondary to the pandemic, we modified our target sample size to 100 patients, aware that the study will provide preliminary nondefinitive data to inform future research. This is consistent with the intent of the catalyst grant that supports the study.

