Objective 3. To evaluate the role of coping abilities and expectations, as measured by the SPOC questionnaire, we will first analyze the association between baseline SPOC and baseline cognitive performance in a traditional multivariable linear regression analysis; similarly, we will analyze the association between early postoperative (4-6 weeks) SPOC and cognitive performance, after adjusting for baseline measurements. Then we will analyze whether preoperative and postoperative SPOC predict cognitive decline at 6 and 12 months using linear and logistic (i.e. with ≥ 2 point decline in MoCA as binary outcome) regression models.

All the analyses for all the objectives will be first conducted in the overall sample of study participants. As additional analysis, we will explore whether there is a signal for any subgroup effect based on the type of surgery performed, i.e., knee versus hip arthroplasty. We will undertake such exploratory subgroup analyses as long as both subpopulations reach at least 30% of representation.

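### At the revised target of 100, the Objective 3 logistic models of MoCA decline would rest on about 20 events, and the plan neither limits covariates by events nor names a small-sample estimator

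*Combined protocol and SAP*

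**What the plan says.** Section 3.6, Objective 3, asks whether SPOC scores before and after surgery predict cognitive decline at 6 and 12 months. It plans linear and logistic regression, the latter "with ≥ 2 point decline in MoCA as binary outcome". It names no covariates and no estimation method for the logistic models.

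Section 3.5 gives the only event rate for this outcome: "20% of the study participants will experience ≥ 2 point decline in MoCA at 1 year". It then records the reduction from at least 150 participants: "we modified our target sample size to 100 patients". Neither the expected number of events nor the power is restated at 100.

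Under Objective 1, section 3.6 gives example covariates for the mixed models: age, sex, comorbidity index, anxiety/depression level and pain medications. Selection is to be parsimonious, guided by clinical relevance and a variance inflation threshold of 2.5. Nothing in 3.5 or 3.6 ties the number of parameters to the number of events, or provides for penalised or exact estimation.

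**The concern.** Maximum likelihood estimates in logistic regression have a small-sample bias away from an odds ratio of 1. The bias grows as events become fewer and parameters more numerous. Reducing the target from 150 to 100 removes a third of the expected events, yet the analysis section makes no allowance for this.

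Section 4 says that the study should inform larger confirmatory work. If an exaggerated odds ratio were carried into the sample-size calculation of such a study, that study would tend to be too small. The linear model fitted alongside does not correct an odds ratio that is reported.

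**Working it through.** **The plan's own figure.** Section 3.5 claims at least 80% power at 150 or more, "with an Odds Ratio of 2.5-3.0", with 20% declining, "30% will present moderate-severe CPSP at 6 months", and R² up to 0.3 between the exposure and the other covariates. I used the Hsieh formula for a binary predictor with N multiplied by (1 − R²). Two-sided alpha of 0.05 is assumed, because none is stated.
- An overall rate of 20% with 30% exposed and an odds ratio of 2.5 implies 15.3% declining in the unexposed and 31.1% in the exposed. Check: 0.7 × 0.153 + 0.3 × 0.311 = 0.20.
- At N = 150 and R² = 0.3, the effective N is 150 × 0.7 = 105. Power is 46% for an odds ratio of 2.5 and 60% for 3.0. At R² = 0 it is 59% and 74%.
- At N = 100 and R² = 0.3, power is 34% and 45%.

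The stated power is therefore not reproduced over its stated range. That is a separate matter, and the point here does not depend on it.

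**Events** (N × rate; N and rate from section 3.5).
- Superseded size: 150 × 0.20 = 30.
- Revised size: 100 × 0.20 = 20.
- With 10% or 20% lacking the 12-month MoCA (assumed; no MoCA attrition figure is given): 90 × 0.20 = 18 or 80 × 0.20 = 16.
- At the 30% rate that section 1 quotes from an older cohort: 100 × 0.30 = 30.
- At 6 months: not computable, as no rate is given.

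**Bias of maximum likelihood.** Data were simulated at N = 100 with 20% events, 3,000 data sets per scenario. The exposure had R² = 0.3 with the covariates and was either binary at 30% or continuous per SD. Half the covariates were binary, and each covariate coefficient was 0.3. Slopes count the predictor plus the covariates.

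| Slopes | Events per slope | Mean excess of the log odds ratio |
|---|---|---|
| 2 | 20/2 = 10 | 3–7% |
| 6 | 20/6 = 3.3 | 8–15% |
| 8 | 20/8 = 2.5 | 15–21% |

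With six slopes, the geometric-mean odds ratios were:

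| True | Maximum likelihood | Firth |
|---|---|---|
| 2.0 | 2.22 | 2.02 |
| 2.5 | 2.69 | 2.47 |
| 3.0 | 3.44 | 3.06 |

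For example, ln 2.22 / ln 2.0 = 0.798 / 0.693 = 1.15, an excess of 15%. At a true odds ratio of 1.0 the mean was 0.98, so there was no material bias.

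**A predictor closer to SPOC.** A further simulation (1,500 data sets) used a continuous predictor with an odds ratio of 2.0 per SD, three covariates and N = 100. Maximum likelihood had 11% bias and a root mean squared error of 0.43. Firth had 1% and 0.38. With one covariate, maximum likelihood bias was about 2 to 8% across scenarios. At N = 80 (about 16 events), with six slopes and the same odds ratio, bias was 18% for maximum likelihood and −1% for Firth.

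**Bias against imprecision.** In the six- and eight-slope models the SD of the estimated log odds ratio was 0.37 to 0.75. A 95% interval then spans a factor of exp(2 × 1.96 × 0.37) ≈ 4 to exp(2 × 1.96 × 0.75) ≈ 19. Wald intervals covered at 94 to 95%, and separation or non-convergence occurred in at most about 0.2% of runs.

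**The case against.** The strongest reply is that a heavily adjusted logistic model is not in the plan. Objective 3 lists no logistic covariates. The list under Objective 1 belongs to mixed models, is introduced as examples and comes with a parsimony rule. Its pain-medication term is time-varying, which fits a longitudinal model better than a single-endpoint one. The odds ratio of 2.5 to 3.0 concerns a binary pain exposure, not SPOC, and no SPOC effect size is given. The bias is also small beside the imprecision, and the linear model is already planned and named first. The study is described as exploratory and nondefinitive, and no section says that a SPOC odds ratio will be used to size a later study.

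Most of this stands, and it limits the claim. A reader might infer that the named covariates by themselves exceed what 20 events can support. The documents do not commit the logistic models to those covariates, so a figure near 3 events per parameter is conditional.

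Two things remain. The parsimony rule works through clinical relevance and collinearity, and neither limits parameters by events. Firth's method also reduced both bias and root mean squared error in every scenario compared, including continuous predictors with few covariates. It is therefore the better default whichever covariate set is chosen.

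**Conclusion.** The point holds in a limited form. About 20 events are expected at 12 months, with 16 to 30 plausible under the attrition and event-rate assumptions above. If several covariates are included, ordinary maximum likelihood would on average exaggerate a non-null log odds ratio by roughly 5 to 20% at N = 100. With one covariate this is about 2 to 8%. These sizes depend on the simulated covariate structure and on effect sizes that the plan does not give for SPOC.

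Two stronger readings should be avoided.
- It does not follow that the reported odds ratios will be too high. The bias is an average tendency away from 1: it is not material at 1, it would push a protective odds ratio too low, and any single estimate can err either way.
- Nor does it follow that the planned inference is invalid, since interval coverage was adequate and fitting failures were rare at N = 100.

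This is a cheap improvement to a secondary exploratory model. It is not a flaw in the primary analysis.

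**What to change.** Add to section 3.6, Objective 3, wording to this effect: logistic models of MoCA decline of 2 points or more will be fitted by Firth's penalised likelihood with profile-likelihood intervals; the covariates will be a short set fixed before analysis and limited by the expected number of events; and the results will be reported as supportive of the linear model.

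Section 3.5 could usefully state the expected number of events at 100.

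The cost is one sentence and standard software. Reported odds ratios will lie slightly closer to 1. The intervals will remain wide, because no estimator makes up for 20 events.

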4. IMPORTANCE OF THE STUDY

“My father hasn’t been quite the same since his surgery...” As doctors, and as children, many of us have had and reported such experience. Anesthetic-related mortality has decreased 100-fold over the last 100 years. However, when asked about their fears related to undergoing major surgery with general anesthesia, people, across different ages, indicate ‘brain damage’ and ‘memory loss’ as main concerns, much more frequently than perioperative death.³⁷ Moreover, the literature shows that, even with only a partial understanding of the concept of likelihood, most older people would not choose a treatment when the expected outcome is survival, if associated with cognitive and functional impairment.^{38 39} CPSP is highly prevalent in older people undergoing surgery, and in particular major orthopedic surgery; in the older surgical populations, also persistent postoperative cognitive dysfunction is highly prevalent. Both these conditions are associated with reduced autonomy and increased burden to patients, caregivers, and healthcare systems.

On the other side, the existing literature shows a decrease in quality of life in people with chronic pain waiting for >6 months for assessment;⁴⁰ and that people waiting for their major joint surgery tend to report that their waiting time is contributing significantly to the deterioration of their health.⁴¹ Likewise, the current experience with COVID and the deferral of elective surgeries is bringing to our attention what holding such treatment might mean to older people with chronic conditions. Our study will provide preliminary data on the role of chronic pain, and chronic pain medications, in the impact of surgery on older people’s cognitive abilities, and on the underlying mechanisms. It will inform larger confirmatory studies, and finally the design of interventions to enhance the benefits of surgery.

APPENDIX I. Study timeline, measurements, and data collection

Measurement	Before surgery		Day of surgery (2-4 hours after surgery)	After surgery			
	Day -28 to -1	Day of surgery		+4-6 weeks	+3 mo	+6 mo	+12 mo
	Online - Videoconference with research team or in person	In person	In person	Online - Videoconference with research team or In person			
Socio-demographics	x						
Comorbidities/ Medical History	X						
Surgical characteristics				x			
Pain Medication Usage	x			x	x	x	x
The Somatic Preoccupation and Coping (SPOC) Questionnaire	x			x			
FRAIL Scale (Frailty assessment)	X						
Hospital Anxiety and Depression Scale (HADS)	X						
Pain Assessment	x			x	x	x	x
Self-Administered Patient Satisfaction (SAPS) Scale					x	x	x
Complications				x	x	x	x
Cognitive/ neuropsychological assessment - MoCA - MST	x			x		x	x

- Other neuropsychological testing - SMC							
Blood drawing for biomarker study		x	x*	x**		x**	x**

*the subset of patients that stay in hospital at least one night after surgery will have blood collected also every morning on postoperative day 1-3, or until discharge (whichever comes first)

**whenever an in person study visit is feasible depending on restrictions in place due to the pandemic and patient compliance
MoCA, Montreal Cognitive Assessment; MST, Mnemonic Similarity Task; SMC, Subjective Memory Complaints

REFERENCES

4. Neuro VI. Perioperative covert stroke in patients undergoing non-cardiac surgery (NeuroVISION): a prospective cohort study. *Lancet* 2019;394(10203):1022-29. doi: 10.1016/S0140-6736(19)31795-7
